1.1 Scope

This document is a supplement to the BACE-N protocol (ClinicalTrials.gov Identifier: NCT04261309) and comprises a SAP for the article “Healthcare utilization and related cost among older people seeking primary care due to back pain: a prospective cohort study with one year of follow up”. The current SAP has been written while data collection was ongoing (we had access to baseline data, but not to follow-up data) and it will be uploaded to the ClinicalTrials.gov before full access to the study database.

2. Administrative information

Version of SAP

1.0

Study sponsor

Oslo Metropolitan University, the Norwegian Fund for Post-Graduate Training in Physiotherapy and “Et liv i bevegelse” (A life in movement) - Norwegian chiropractors’ research foundation

Names, affiliations and roles of SAP contributors

Name	Title	Affiliation	Role
[name]	[name] University [name] [contact] Email: [contact]	Principal Investigator
[name]	PhD-student	Oslo Metropolitan University	Main author of SAP
[name]	[name] University	Contributor to SAP
[name]	[name]	Contributor to SAP
[name]	[name] University	Statistical advisor
[name]	PhD-student	Oslo Metropolitan University	Contributor to SAP
[name]	PhD-student	Oslo Metropolitan University	Contributor to SAP

Signatures: person writing SAP, senior statistician and principal investigator

[name]

Main author of the SAP

[name]

Senior statistician responsible

[name]

Principal Investigator

3. Study aim

The primary aim of this study is to describe healthcare utilization and estimate associated costs during one year of follow up of older people seeking primary care due to a new episode of back pain. The secondary aim is to describe frequency of healthcare utilization across patients with different risk profile stratified according to the StarT Back Screening tool.

4. Study design, population and method

Study design

A prospective observational cohort study with one year of follow-up within a Norwegian primary care setting.

Study population and recruitment

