Eligible patients are people 55 years of age or older who seek primary care (physiotherapist, chiropractor or GP) with a new episode of back pain (preceded by 6 months without visiting a primary care provider for similar complaints). Patients are excluded if they have difficulties completing the questionnaires (e.g. unable to speak, read or write in Norwegian) or if they have difficulties completing the physical examination (e.g. are wheelchair bound).

Patients were recruited from physiotherapists, chiropractors and GPs working in Norwegian primary care between April 2015 and February 2020. Patients who met the eligibility criteria and completed the consent to participate were included in the study.

Method

At baseline all patients completed a comprehensive questionnaire and underwent a standardized physical examination conducted by local research assistants at test stations established within each recruiting area. Follow-up questionnaires will be sent at 3, 6, and 12 months after inclusion for completion at home. All questionnaires are preferably completed electronically using the Infopad system, but paper versions will be available for patients not familiar with electronic data collection. All information will be stored and analysed securely through Service for sensitive data (TSD) at the University of Oslo, Norway.

Variables

Outcome variables

The primary outcome of this study is total costs of healthcare utilization (summed up for one year of follow-up). The secondary outcome is frequency of healthcare utilization (summed up for one-year of follow-up across patients with different risk profile according to the StarT Back Screening tool).

Healthcare utilization will be self-reported, collected through follow-up questionnaires, and include; consultation to healthcare professionals (type and frequency), number of diagnostic examinations (type and frequency), number of days of hospitalization and/or institutionalisation, back operations and use of back medication (both prescription and over-the-counter, type and frequency). All variables, except the “operation” variable, will be

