Next, costs will be estimated based on information presented in table 3 and unit costs of healthcare resources collected from national pricelists (see table 1). Costs related to back medication will be estimated based on medication type (not exact medication name) and frequency of use. Data on dosage is not available. All costs will be presented in Norwegian Krones (NOK) and euros (€) 2020. Costs of healthcare utilization will be described with median and interquartile range for each follow-up period and for the whole year as shown in table 4. If data is highly skewed, bias-corrected and accelerated bootstrapping will be considered to derive confidence intervals for cost estimates.

Secondary analysis

First, type and frequency of different healthcare resources will be described for the one-year of follow-up for the following subgroups: (1) low, (2) medium, and (3) high risk of persistent disabling back pain according to the StarT Back Screening tool and presented as shown in table 5.

Next, Kruskall Wallis test will be used to determine whether there is a significant difference between the three subgroups with regards to; number of primary care consultations, number of patients using back medication, number of patients receiving imaging (X-ray, MRI, CT) and number of patients receiving secondary care (back operation, hospitalization, rehabilitation stay). For all analyses, p values of < 0.05 will be considered statistically significant.

Sample size and statistical power consideration

This study contains secondary analyses embedded in the BACE-N study. Details on sample size calculation are provided in the BACE-N protocol (ClinicalTrials.gov Identifier: NCT04261309). With a sample size of 450 participants within the BACE-N study, we assume to have expectable power to describe healthcare utilization and estimate associated costs [17].

Sensitivity analyses

To assess the robustness of the results, the following sensitivity analyses will be carried out for cost calculations related to the primary analysis:

1. Complete case analysis (without using imputation for missing data)
2. Without outliers (outliers will be identified with simple scatter plots by visual inspection)

6. Selection bias, information bias and confounding

Selection bias:

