Back medication			
Patients with use of back medication, N (%)			
Paracetamol			
NSAID			
Muscle relaxants			
Sleep medication			
Cortisone			
Opioid			
Others			
Frequency of use paracetamol, N (%)			
Daily			
Weekly			
Monthly or less			
Frequency of use NSAID, cortisone N (%)			
Daily			
Weekly			
Monthly or less			
Frequency of use muscle relaxants, sleep medication, N (%)			
Daily			
Weekly			
Monthly or less			
Examinations			
Patients with additional diagnostic examination, N (%)			
Blood sample			
X-ray			
MRI			
CT			
Secondary care			
Patients with back operation, N (%)			
Patients with hospitalization, N (%)			
Duration of stay in days, median (IQR)			
Patients with rehabilitation stay, N (%)			
Duration of stay in days, median (IQR)			

Table 4 Cost due to healthcare utilization from 0-3 month, >3-6 months, >9-12 months and the entire follow-up period (0-12 month)

	0-3 months	3-6 months	>9-12 months	0-12 months*
Primary care				
General practitioner				
Physiotherapist				
Chiropractor				
Manual therapist				
Naprapath				
Osteopath				
Psychologist				
Other therapists				
Back medication				
Paracetamol				
NSAID, cortisone				
Muscle relaxants, sleep medication				
Examinations				
Blood sample				
X-ray				
MRI				
CT				
Secondary care				
Back operation				
Hospitalization and/or rehabilitation stay				
Total costs				

Values are median (interquartile range) of costs (€). *Cost due to healthcare utilization for the entire follow-up period is calculated on the basis for the three follow-up periods

Table 5 Healthcare utilization throughout one-year of follow-up, across patients with different risk profile according to the StarT Back Screening tool

	Stratified risk profile		
	Low (n = x)	Medium (n = x)	High (n = x)
Primary care			
Patients with primary care consultation, N (%)			
Number of primary consultations, median (IQR)			
Back medication			
Patients with use of back medication, N (%)			
Paracetamol			
NSAID			
Muscle relaxants			
Sleep medication			
Cortisone			
Opioid			
Examinations			
Patients with additional diagnostic examination, N (%)			
Blood sample			
X-ray			
MRI			
CT			
Secondary care			
Patients with back operation, N (%)			
Patients with hospitalization, N (%)			
Patients with rehabilitation stay, N (%)			

[figure not shown]

Figure 1. Flow chart of the study

References

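### SAP 1 names frequency of use by StarT Back group as its secondary outcome, but Table 5 and the tests reduce medication and imaging to any use

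*Combined protocol and SAP*

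**What the plan says.** All references are to SAP 1, on healthcare utilization and costs.

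- **Study aim (section 3).** "The secondary aim is to describe frequency of healthcare utilization across patients with different risk profile", stratified by StarT Back.
- **Outcome variables (section 4).** "The secondary outcome is frequency of healthcare utilization (summed up for one-year of follow-up" by StarT Back group). Data collection covers "use of back medication (both prescription and over-the-counter, type and frequency"), and diagnostic examinations are likewise collected by type and frequency.
- **Secondary analysis (section 5).** Type and frequency are to be described by risk group in Table 5. Then: "Next, Kruskall Wallis test will be used to determine whether there is a significant difference between the three subgroups". The tested variables are "number of primary care consultations", followed by "number of patients using back medication, number of patients receiving imaging (X-ray, MRI, CT) and number of patients receiving secondary care". The threshold is p < 0.05.
- **Table 3.** By follow-up period, it separates the number of patients using medication from rows such as "Frequency of use paracetamol, N" (%), split into daily, weekly, and monthly or less.
- **Table 5.** By risk group, consultations have a median (IQR). Medication, examinations and secondary care have N (%) of patients only.

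**The concern.** The SAP asks how often each risk group uses care. For medication and imaging it then tests, and tabulates by risk group, only whether a patient used the resource at all. A patient who takes a drug monthly or less is tied with one who takes it daily all year.

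If most patients in this care-seeking cohort take some medication during the year, the yes/no variable has little room to differ between groups. A real gradient in intensity could then be reported as no difference. The graded data that would show it are collected, but they appear only in Table 3, by period and not by risk group.

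**Working it through.** **1. Collected, displayed and tested**

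| Resource | Collected | Table 5 | Tested as |
|---|---|---|---|
| Primary care consultations | type and frequency | N (%) and median (IQR) | count |
| Back medication | type and frequency | N (%) | any use |
| Imaging | type and frequency | N (%) | any use |
| Secondary care | operations; days of stay | N (%) | any use |

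Only the first row carries the named outcome through to the analysis.

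**2. What the test sees**

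The tie-corrected Kruskal-Wallis statistic is H = [12/(N(N+1))] Σ n_g (R̄_g − (N+1)/2)² ÷ [1 − Σ(t³ − t)/(N³ − N)], compared with chi-square on 2 df. On a 0/1 variable it equals (N−1)/N times Pearson's chi-square. A numerical check gave 5.397 both ways, and null rejection was about 5% for both codings. The planned test is valid, but it compares proportions of users and uses no frequency information.

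**3. Inputs for power**

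From the documents: N = 450, two-sided alpha 0.05, three groups. The comorbidity SAP expects about 380 participants at 12 months. SAP 1 gives no user rate, frequency distribution, effect size, group size or power figure for this comparison (Table 5 has n = x), so there is no plan figure to reproduce and everything else below is assumed. The main case uses groups of 50/35/15% and proportional odds of 1, 1.5 and 2.25 across low, medium and high risk.

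**4. Why the share of users matters**

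Any use, from odds = p/(1−p):
- 30% in the low-risk group: odds 0.429. Times 1.5 = 0.643, or 39%. Times 2.25 = 0.964, or 49%. Spread low to high: 19 points.
- 85% in the low-risk group: odds 5.667. Times 1.5 = 8.5, or 89%. Times 2.25 = 12.75, or 93%. Spread: 8 points.

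In the second case, suppose low-risk users are spread evenly over the three frequency categories. Daily use is then 0.85/3 = 28%, with odds 0.395. Times 1.5 = 0.593, or 37%. Times 2.25 = 0.889, or 47%. That is a spread of 19 points which the yes/no variable does not see.

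**5. Simulated power (8,000 runs per scenario, N = 450, 50/35/15%)**

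| Users in low-risk group | Yes/no | Four-level frequency | Change (points) |
|---|---|---|---|
| 30% | 78% | 81% | +3 |
| 50% | 78% | 87% | +9 |
| 70% | 63% | 88% | +25 |
| 85% | 34% | 88% | +54 |
| 92% | 17% | 87% | +70 |

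A rerun with low-risk users spread evenly over the categories agreed to within about a point. At N = 380 with a 45/40/15% split the pattern is the same: 69% against 72% at 30% users, and 29% against 80% at 85%.

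**6. Departures from proportional odds (N = 450, 50/35/15%)**

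- 70% users in every group, strong shift in frequency: 5% (yes/no) against 47% (frequency).
- Users 60/70/80%, same frequency among users: 86% against 71%, a loss of about 14 points.
- Users 75/82/90%, same frequency among users: 75% against 43%, a loss of 32 (3,000 runs).
- Users 60/70/80%, less daily use at higher risk: 86% against 6%, a loss of 80.

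Over all assumed scenarios, group splits and both sample sizes, the change runs from about −84 to +79 points.

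**7. The other resources**

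One scenario each, 20,000 runs:
- Imaging, any use 20/27/35%: 66% (yes/no) against 69% (count).
- Secondary care, 3/5/10%: 54% against 55%.

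**The case against.** **The aim is to describe, and Table 5 itself presents N (%) as the one-year summary by risk group.** The proportion of users is a legitimate quantity, and frequency can be read loosely as the number of users. This explains the layout but does not settle the matter. Table 3 treats users and frequency of use as separate quantities, the Secondary analysis goes on to significance testing, and Table 5 lacks frequency rows even as description.

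**A frequency test is not always the stronger test.** This stands. Proportional odds favours a graded scale. If the groups differ in whether they use medication but not in how often users take it, the yes/no test wins, even where use is common (75/82/90% above). The documents give no figure showing that use is near its ceiling.

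**A one-year medication score is not ready-made.** This also stands. Table 3 has no frequency row for opioids or for the category of other drugs, although both have user rows. Dosage is not available. A simple sum over follow-ups would tie daily use in one period (3+0+0) with use monthly or less in all three (1+1+1). The simulated variable was a single four-level scale, so no power figure here applies to a summed score. On the other side, the primary analysis already costs medication from type and frequency, so frequency has to be turned into patient-level amounts in any case.

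**Stronger readings a reader might infer.** One is that the plan gives up a definite amount of power, for instance from the assumed case of a 45/40/15% split, 85% users and odds ratios 1/1.7/2.9 (52% against 98%). That is one scenario, neither a bound nor derivable from the SAP. Another is that Kruskal-Wallis on yes/no data is wrong, which step 2 contradicts. A third is that the yes/no tests should be replaced, which the reversals argue against.

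**Conclusion.** The point holds as a mismatch between outcome and analysis. For medication and imaging, the named secondary outcome is neither tested nor tabulated by risk group, although the data are collected. The practical risk lies with medication, where a gradient in intensity could go unseen.

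Its size cannot be fixed from the documents. Under proportional odds of 1.5 per risk step (N = 450, 50/35/15%), a frequency scale gains about 3 points of power at 30% users in the low-risk group and about 54 at 85%. The sign reverses if the groups differ mainly in any use. For imaging (+3) and secondary care (+1) the effect on power is negligible in the scenarios tried. The case for change therefore rests on answering the stated question, with power as a possible added benefit.

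**What to change.** In SAP 1, Secondary analysis and Table 5:

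1. Keep the N (%) rows and the existing ever/never comparisons.
2. Add to Table 5, by risk group, the medication frequency categories (none, monthly or less, weekly, daily) and the number of imaging examinations.
3. Add a Kruskal-Wallis test of one prespecified patient-level medication-frequency variable, identified as the test that matches the named outcome.
4. State in advance which drugs that variable covers, including how opioids and other drugs are handled, and how the three follow-ups are combined.
5. Secondary care may stay yes/no.

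The cost is a few lines of SAP text, some table rows, one more test and a scoring rule to fix in advance. It needs no new data or software.

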reported with a 3 month recall period at 3, 6, and 12 months follow-up. The “operation” variable will be reported with a 12 month recall period at 12 months follow-up. Healthcare utilization during the one year of follow-up will be described as shown in table 3 and table 5. The total cost of healthcare utilization will be estimated based on information presented in table 3 and unit costs of healthcare resources collected from national pricelists (see table 1).

Screening tool

The Keele StarT Back Screening Tool (SBST) [1] will be used to classify the included patients into low, medium or high risk of poor disability outcome. The SBST is a brief 9-item tool designed to screen primary care patients with low back pain for prognostic indicators that are relevant to initial decision making. The tool is summed to produce an overall score from zero to nine and a psychological subscale score from zero to five. Patients with an overall score between 0-3 are classified as low risk. Patients with an overall score of minimum 4 and a subscale score of maximum 3 are classified as medium risk. Patient with an overall score of minimum 4 and a subscale score of 4 or 5 are classified as high risk. The SBST was translated into Norwegian by [name] and [name] in 2012, and has shown to have an acceptable accuracy in distinguishing between low back pain patients who have recovered or not after 1 year of follow-up [2].

Other variables

Included patients will be described with respect to the following baseline characteristics: age, gender, ethnicity, educational level, first healthcare provider, pain location, pain severity, pain duration, pain history, disability, comorbidity, health-related quality of life, emotional well-being, kinesiophobia and healthcare utilization six weeks prior to inclusion (table 2).

The Numeric Rating Scale (NRS) will be used to measure average pain severity last week [3]. The NRS, scored from 0 (no pain) to 10 (maximum pain), has been widely used to evaluate pain and has proven to be preferable when examining low back pain patients [4], also for Norwegian patients [5].

The Roland Morris Disability Questionnaire (RMDQ) [6] will be used to measure disability. The RMDQ is a widely used back-specific patient-reported measure of pain-related disability (0 = no disability, 24 = totally disabled). The Norwegian version has been validated and found to have good measurement properties when used among patients with low back pain [5, 7].

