All analyses described in this plan are considered a priori in that they have been defined in the protocol and/or in this SAP. All post hoc analyses will be identified as such in the article if relevant. All analyses will be carried out by a PhD-student using SPSS version 26 and controlled by a senior researcher/statistician. All statistical tests will be two-sided, and nominal p-values will be reported. Preliminary analyses assessing the influence of missing data and assumptions of normality for continuous variables will be conducted. The assumption of normal distribution will be investigated using histograms and QQ-plots. Normally distributed data will be presented with means and standard deviations (SDs), skewed data with medians and interquartile range (IQR). Categorical data will be reported as counts and percentages. Missing data will be handled by multiple imputation, using 5 imputations and 10 iterations unless the missingness exceeds 30% and/or missing at random cannot be assumed. Fully conditioned specification method and regression estimation will be used. For variables where we are unable to use regression estimation due to computational difficulties, predictive mean matching will be used [15].

Description of study flow

The flow of participants through the study will be reported according to the STROBE guidelines [16] with a flow chart (see figure 1). Reasons for dropout will be provided where known. Differences between responders and non-responders will be evaluated.

Participant characteristics

Baseline characteristics of included patients will be presented for the whole sample and the following subgroups: (1) low, (2) medium, and (3) high risk of persistent disabling back pain according to the StarT Back Screening tool (see table 2).

Primary analysis

First, type and frequency of different healthcare resources will be calculated for each of the follow-up periods; from baseline to 3 months, 3 to 6 months, and 9 to 12 months and presented as shown in table 3.

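### The cost SAP labels its primary outcome a one-year cost, but every item except back operations is observed for only 9 of 12 months and no rule is given for months 6-9

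*Combined protocol and SAP*

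**What the plan says.** The point concerns the first SAP in the combined document (healthcare utilization and related cost), called the cost SAP here.

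- **Aim (section 3):** to describe utilization and "estimate associated costs during one year of follow up".
- **Outcome (section 4, Outcome variables):** "The primary outcome of this study is total costs of healthcare utilization (summed up for one year of follow-up").
- **Measurement (same section):** all items except operations are "reported with a 3 month recall period at 3, 6, and 12 months follow-up". For operations, the "variable will be reported with a 12 month recall period at 12 months follow-up".
- **Primary analysis (section 5):** use is tabulated "from baseline to 3 months, 3 to 6 months, and 9 to 12 months". Costs are then "described with median and interquartile range for each follow-up period and for the whole year as shown in table 4".
- **Table 4:** three quarterly columns (none for months 6-9) and a 0-12 month column, with the footnote "Cost due to healthcare utilization for the entire follow-up period is calculated on the basis for the three follow-up periods".
- **Missing data and sensitivity (section 5):** multiple imputation is planned unless missingness exceeds 30% and/or missing at random cannot be assumed. The two sensitivity analyses are complete case and exclusion of outliers.
- **Table 5:** one-year utilization by StarT Back risk group, built from the same questionnaires.

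**The concern.** The label says twelve months, while the questionnaires cover nine for everything except operations. The cost SAP does not say whether months 6-9 are left out, interpolated or scaled. Because the outcome is described as a sum over the year and the footnote rests it on three periods, a plain sum is the natural reading.

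The study is descriptive, so the level of annual cost is itself the result and there is no contrast in which a missing quarter could cancel. Leaving the formula open also means it could be chosen after the costs are seen, and the candidate formulas give materially different totals. Table 5's one-year user percentages and consultation counts share the same gap.

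**Working it through.** **1. Months covered.** Windows from the Primary analysis section: (3-0) + (6-3) + (12-9) = 9 months, and 9/12 = 75%. The label's 12 months is not reproduced. Two checks do give 12: back operations alone (12-month recall), and the Dutch cohort in the second SAP (four windows, 4 x 3 = 12).

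**2. What a plain sum contains.** With C for non-operation cost:

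- plain total = C(0-3) + C(3-6) + C(9-12) + operations(0-12)
- annual total = plain total + C(6-9)

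C(6-9) cannot be negative, so this component of the error has one sign.

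**3. Does anything else in the cost SAP fill the gap?** Multiple imputation is for unanswered items. Months 6-9 were not asked about, so missingness there is 100% against a 30% limit. Both sensitivity analyses use the same three windows.

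**4. Size for the non-operation mean.** The documents hold no cost data, so the quarter shares are assumptions. Plain-sum shortfall = third-quarter share. Error after filling with the neighbours' mean = (Q2 + Q4)/2 - Q3.

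| Assumed shares (%) | Plain sum | Neighbour mean |
|---|---|---|
| 25/25/25/25 | -25% | (25+25)/2 - 25 = 0 |
| 60/20/10/10 | -10% | (20+10)/2 - 10 = +5% |
| 80/12/5/3 | -5% | (12+3)/2 - 5 = +2.5% |
| 33/17/33/17 (stress test) | -33% | -17% |

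**5. Size for the median, which Table 4 plans to report.** Simulation with 400,000 patients, lognormal quarterly costs, CV 2, between-quarter correlation 0.3 or 0.6, with and without zero-cost quarters. The ranges below hold without operations; placing operations in 2% of patients barely moves the median.

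- Plain sum, 25/25/25/25 to 60/20/10/10: median about 10-29% too low.
- Plain sum, 80/12/5/3: median about 6-8% too low, so 10% is not a floor.
- Plain sum, third-quarter rise (stress test): median about 25-37% too low.
- Neighbour mean, 25/25/25/25 to 60/20/10/10: median -5% to +4% without zero-cost quarters and down to about -14% with many; lower quartile down to about -21%.
- Neighbour mean, third-quarter rise: median about 14-20% too low.

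A single Table 4 row used by fewer than half of patients over the year has a median of 0 with or without months 6-9. The effect shows in the total and in the commonly used items.

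**6. Why not multiply everything by 12/9.** Operations already cover the year. With flat non-operation cost and operations a share f of the plain sum, the true year is f + (1-f) x 4/3. At f = 0.3 this is 1.233: the plain sum is 1 - 1/1.233 = 18.9% short, while blanket scaling overstates by 1.333/1.233 - 1 = 8.1%.

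**7. Table 5 percentages.** With an assumed 5% of patients using a resource in each quarter, independently: 1 - 0.95^3 = 14.3% over 9 months against 1 - 0.95^4 = 18.5% over 12. If the same patients tend to be users each quarter the gap shrinks: 11.1% against 13.3% at latent correlation 0.6, and 8.0% against 8.8% at 0.9.

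**The case against.** The strongest defence is disclosure. The text, the table headings and the footnote all show three periods, and no cost hypothesis is tested. The footnote's wording also permits extrapolation. The SAP states that its analyses are a priori because "they have been defined in the protocol and/or in this SAP", and the separate BACE-N protocol is not among these documents, so a rule may exist there. This stands as far as it goes: a plain sum is the natural reading but not an established one. What is certain is that this SAP states no rule for a figure it labels annual.

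A reader might infer several stronger things that the documents do not support:

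- **That the total is purely a 9-month cost.** It is not; operations are recalled over 12 months, so the total mixes windows.
- **That no patient's total can exceed the true cost.** Use is self-reported, medication is priced without dosage, and missing answers are imputed. Each can push a total upwards. Only the omitted window has a fixed sign.
- **That the shortfall is a third or more.** That needs use to peak in exactly the unobserved quarter, for which the documents give no support.
- **That the risk-group comparison is invalid, or wholly unaffected.** Shared windows keep the 9-month comparison fair. A one-year comparison also assumes that months 6-9 follow the same group pattern.

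In the second SAP (prognostic factors of high cost) the three-versus-four-period difference is disclosed and high cost is the top quarter within each cohort, so the point is minor there.

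**Conclusion.** The point holds in this form: the primary outcome carries a 0-12 month label, all items except back operations are observed for 9 of 12 months, and the cost SAP gives no rule for the rest. Read as a plain sum, it understates annual non-operation cost, apart from recall, pricing and imputation error. The missing rule and that direction are secure. The percentages are not: the median shortfall of about 6-29% rests entirely on assumed quarter shares from flat to 80/12/5/3, lognormal costs and CV 2. Severity is should-fix. The windows are disclosed and months 6-9 cannot be recovered, but the label on the main result does not match what was measured.

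**What to change.** Choose one and write it into the cost SAP.

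**(a) Relabel.** Describe the outcome, the Table 4 whole-year column and the Table 5 rows as 9 observed months (0-6 and 9-12), with back operations over 12 months. This is wording only and needs no assumption. The cost is that no full-year figure is reported.

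**(b) Keep the one-year cost label.** Within each imputed dataset, set each 3-month-recall item's cost in months 6-9 to the patient's mean of the 3-6 and 9-12 month costs (medication after conversion from frequency category to cost). Enter operations once, unscaled. Report the observed sum as a sensitivity analysis. This is one sentence and a few lines of code. The downside is an interpolation assumption that, with many zero-cost quarters, can leave the median about 14% and the lower quartile about 21% too low. Cost and utilization would also then cover different periods.

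Under either choice, label Table 5 utilization other than operations as 9 observed months and do not interpolate events. State that the tested secondary-care composite combines 12-month operations with 9-month hospitalization and rehabilitation. For the second SAP, an optional sensitivity replication leaving out months 6-9 in the Dutch cohort is enough.
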